9.1. Primary Outcome and Analyses

The primary outcome of each participant is the area under the stimulated C-peptide curve (AUC) over the first 2 hours of a mixed meal glucose tolerance test conducted at the one-year visit. The AUC is computed using the trapezoidal rule that is a weighted sum of the C-peptide values over the 120 minutes. The weighted mean C-peptide is simply AUC/120 (pmol/mL). Let $Y_{Cp}^{GAD\times3}$, $Y_{Cp}^{GAD\times2}$, and $Y_{Cp}^{Control}$ represent the mean C-peptide value for study patients receiving three injections with 20µg GAD-Alum, those receiving two injections with 20µg GAD-Alum and those receiving placebo, respectively. Likewise, let $\mu_{Cp}^{GAD\times3}$, $\mu_{Cp}^{GAD\times2}$, and $\mu_{Cp}^{Control}$ represent the mean of Y_{Cp} for these groups, respectively.

The primary statistical hypotheses to be assessed in the study are:

$$H_{0}: \mu_{Cp}^{GAD\times3} = \mu_{Cp}^{Control} \text{ versus } H_{a}: \ \mu_{Cp}^{GAD\times3} > \mu_{Cp}^{Control}$$
$$H_{0}: \mu_{Cp}^{GAD\times2} = \mu_{Cp}^{Control} \text{ versus } H_{a}: \ \mu_{Cp}^{GAD\times2} > \mu_{Cp}^{Control}$$

The primary analysis will be conducted on the transformed Y_{Cp} using the log function: $\log(Y_{Cp} + 1)$. This provides better normal distributional behavior by the test statistic. The comparison between any two treatment arms will be based on a t-test of treatment effect in an ANCOVA model adjusting for gender, baseline age, and baseline $\log(Y_{Cp} + 1)$ (49).

The Holm closed-sequential procedure for multiple tests (46) will be used to control the type I error probability to not exceed 0.05, one-sided, for the set of two pairwise group comparisons.

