4.6. Treatment Assignment and Double Masking

After participants sign the consent form they will be randomized to one of the treatment arms. The randomization method will be stratified by TrialNet study site. The participants will not be informed regarding the intervention assignment until the end of the study. The investigator and clinic personnel will also be masked as to study assignment. Laboratories performing assays for this protocol will be masked as to the identity of biological material to be studied.

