4.7. Study Assessments

During the course of the study, participants will frequently undergo assessments of their insulin production, immunologic status, overall health and well being and diabetes care (see schedule of assessments in Appendix A). The participant's insulin production will be measured by a series of mixed meal glucose tolerance tests (MMTT) conducted regularly during the study. The participant's diabetes control will be evaluated by measuring glycosylated hemoglobin (HbA1c) every three months and clinical records including insulin types, doses, and timing and SBGM records.

During the course of the study, samples will be drawn for storage in the National Institute for Diabetes and Digestive and Kidney Disease (NIDDK) Repository and at TrialNet Sites for future analysis. These samples will be collected only with the subject's permission. Subjects who decline consent for these sample collections will still be eligible to participate in this study.

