6.2. Laboratory Assessments

The following laboratory assessments will be performed during the study:

- Chemistry (sodium, potassium, chloride, CO2, glucose, BUN, creatinine)
- Liver function tests (ALT, AST, alkaline phosphatase, total protein, albumin, total and direct bilirubin)
- Hematology (complete blood count with differential and platelets)
- Urine pregnancy test as appropriate
- Islet Autoantibodies
- Viral serology: antibodies to HIV, hepatitis B (antiHBcAb, HbsAg,), hepatitis C (HCV),Cytomegalovirus (CMV IgG)) Epstein-Barr Virus (EBV IgG and IgM). Viral load will be determined if indicated.
- PPD
- Samples for titers from routine childhood immunizations.

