The mean HbA1c, insulin dose (units/kg), and blood glucose over all follow-up values will be compared between groups using a normal errors longitudinal analysis (45). The rates of severe hypoglycemic and adverse events will be computed (total number of events divided by total patient years of follow-up) and the rates compared using a Poisson regression model, allowing for over-dispersion using a quasi-likelihood model as appropriate. Both sets of analyses will be adjusted for age, gender, baseline log(C-peptide+1) and baseline HbA1c.

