9.4. Sample Size and Power Calculations

The primary analysis will compare the difference between each treated group separately versus the placebo group (two pair-wise comparisons) in the levels of $\log(Y_{Cp} + 1)$ using an ANCOVA model adjusting for gender, baseline age, and baseline $\log(Y_{Cp} + 1)$. Estimates of the mean and standard deviation of $\log(Y_{Cp} + 1)$ (expressed algebraically as: $\hat{\mu}_{\log(Y_{Cp}+1)}$ and $\hat{\sigma}_{\log(Y_{Cp}+1)}$) in the placebo group were obtained from prior studies. Among patients with baseline C-peptide > 0.2 pmol/ml and \geqq gd2 years, $\hat{\mu}_{\log(Y_{Cp}+1)} = 0.248$ and $\hat{\sigma}_{\log(Y_{Cp}+1)} = 0.179$ (3). An approximation of the mean of Y_{Cp} for the placebo group is calculated by applying the inverse transformation; this yields 0.282 pmo/mL.

Using standard equations for the comparison of two means, a sample size of 38 patients with complete data needed for the primary analysis per group, would provide power of 85% to detect a 60% increase (on the original scale) in the geometric mean C-peptide with either treatment relative to the placebo group using a test at the 0.025 level (one-sided).

Assuming that 10% of the patients will be "lost" (unavailable for the primary analysis), this study will require enrolling 42 eligible patients per group (126 total). The plan is to follow these patients two years from baseline and for up to 2 additional years post-treatment if residual beta-cell function or immunological effects are detected.

TrialNet: GAD Intervention Protocol

The exact final sample size can not be fixed to be exactly because of staggered patient entry. The study will be closed to new patients entering the screening phase when the total number then randomized plus a fraction of those in screening is expected to provide the proper number of eligible patients. Patients who had already conducted the initial screening visit at that time will be allowed to complete screening and be randomized if both consenting and eligible.

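### The primary ANCOVA omits study site, the only randomisation stratum (small cost, and only if sites differ); the insulin-dose and glucose models omit the outcome's own baseline

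*Protocol*

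**What the plan says.** Protocol 4.6: "The randomization method will be stratified by TrialNet study site". No other stratum is named, and neither the number of sites nor a block size is given.

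Protocol 9.1: the comparison of any two arms "will be based on a t-test of treatment effect in an ANCOVA model adjusting for gender, baseline age, and baseline" log(Y+1). Protocol 9.4 gives the same list for the power calculation: "using an ANCOVA model adjusting for gender, baseline age, and baseline" log(Y+1). Site is not a covariate in any model in section 9.

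Protocol 9.2, on three metabolic outcomes: "The mean HbA1c, insulin dose (units/kg), and blood glucose over all follow-up values will be compared between groups using a normal errors longitudinal analysis". The covariates for these models, and for the event-rate models, are then fixed together: "Both sets of analyses will be adjusted for age, gender, baseline log(C-peptide+1) and baseline HbA1c".

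Baseline data: 6.2 includes glucose in the chemistry panel, and the Appendix 1 schedule marks chemistries at the screening visit. Insulin dose is listed as an assessment in 6.4 but has no row in the schedule; 4.7 takes it from "clinical records including insulin types, doses, and timing and SBGM records".

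**The concern.** There are two separate issues, both about covariate lists that the protocol writes out in full. They are therefore stated choices, not details left open for an analysis plan.

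**Site.** Stratifying by site makes the arms more alike in site composition than simple randomisation would, so between-site variation largely cancels from the difference between arms. A model without site still counts that variation as error. The reported standard error is then somewhat too large, the true size falls below the nominal level, and some of the power that stratification offers is not collected. The same t-test feeds the interim and futility rules in 9.5, so the model should be settled before anyone sees unmasked results.

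**Own baseline.** The protocol adjusts C-peptide for baseline C-peptide and HbA1c for baseline HbA1c. For insulin dose and blood glucose it uses the same shared list, which holds neither outcome's own baseline, and gives no reason. Their own baselines are likely to be strong predictors of later values. Without them the comparisons are less precise and more exposed to chance imbalance at entry.

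**Working it through.** **1. Reproduce the planned sample size.** From 9.4: placebo mean of log(Y+1) 0.248, SD 0.179, a 60% increase on the original scale, 38 complete patients per group, one-sided 0.025.

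- Effect on the log scale: ln(1 + 1.6 × (e^0.248 − 1)) − 0.248 = ln(1.4503) − 0.248 = 0.1238.
- SE of the difference: 0.179 × √(2/38) = 0.0411.
- Power: Φ(0.1238/0.0411 − 1.96) = Φ(3.015 − 1.96) = 85.4%.

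This agrees with the stated 85% at 38 per group. The calculation uses the placebo SD as given. It takes no credit for covariates or for site, so leaving site out does not lower the stated power.

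**2. Site omitted, upper bound.** The protocol gives no ICC; the values here are assumptions. Ignore degrees of freedom, assume balance within site, and let site hold a share ICC of the variance 0.179².

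- SE excess without site: 1/√(1 − ICC) − 1.
- True size without site: 1 − Φ(1.96/√(1 − ICC)).
- Power without site: Φ((3.015 − 1.96)/√(1 − ICC)).
- Power with site: Φ(3.015/√(1 − ICC) − 1.96).

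| ICC | SE excess | True size | Power without site | Power with site | Gain (points) |
|---|---|---|---|---|---|
| 0 | 0% | 0.025 | 85.4% | 85.4% | 0 |
| 0.05 | 2.6% | 0.022 | 86.0% | 87.1% | 1.1 |
| 0.10 | 5.4% | 0.019 | 86.7% | 88.8% | 2.1 |

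**3. Site included, by form of the term.** Simulation: 126 patients, three arms, blocks of 3 within sites of unequal size, about 9.5% lost. The number of sites and the block size are also assumptions. The entries are the model SE without site divided by the model SE with site, so a value below 1 means that adding site made the SE larger.

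| Form of site term | ICC 0 | ICC 0.05 | ICC 0.10 |
|---|---|---|---|
| Unpooled fixed, 10 sites | 0.99 | 1.02 | 1.04 |
| Unpooled fixed, 20 sites | 0.98 | 1.00 | 1.02 |
| Unpooled fixed, 30 sites | 0.95 | 0.97 | 1.00 |
| Random intercept, 10 to 30 sites | 1.006–1.010 | 1.024–1.026 | 1.045–1.047 |

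With the random intercept, the power gain was about 1 point at ICC 0.05 and about 2 points at 0.10. At ICC 0 there was no penalty (84.5–84.7% without site, 84.8–85.0% with). Simulated size with the random intercept was 0.020 to 0.029 against 0.025, with a Monte Carlo error of about 0.0025.

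**4. Own baseline omitted.** Let ρ be the correlation of the outcome's baseline with its mean over follow-up, after the listed covariates. The protocol gives no value, so ρ is an assumption. Including the baseline multiplies the SE by √(1 − ρ²); leaving it out gives up a share ρ² of the effective sample size.

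| ρ | Cut in SE from adding baseline | Effective sample lost without it |
|---|---|---|
| 0.3 | 1 − √0.91 = 4.6% | 9% |
| 0.5 | 1 − √0.75 = 13.4% | 25% |
| 0.7 | 1 − √0.51 = 28.6% | 49% |

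**The case against.** The case against the site issue is substantial. The protocol gives no site count and no between-site variance. C-peptide appears to be measured centrally (4.8 refers to central laboratories), and baseline C-peptide, age and gender are already in the model, so the remaining ICC could be close to zero. The formula in step 2 is a best case: 126 patients spread over unequal sites leave incomplete blocks, so within-site balance is imperfect. It also applies the ICC to 0.179, which 9.4 does not describe as a covariate-adjusted SD. Any error is conservative, and the gain is a point or two of power. With unpooled fixed site effects the remedy can do harm: with 30 sites it raises the SE by about 5% at ICC 0 and only breaks even near 0.10.

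Most of this stands and limits the claim. It does not remove it, because the penalty belongs to unpooled fixed effects; the random intercept showed none at ICC 0.

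On the own baseline, it is fair to say that these are two items in a long secondary list, that baseline HbA1c and C-peptide may recover part of the loss (glucose especially), and that a baseline insulin dose must first be defined. None of this is a reason to leave the baseline out.

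A reader might infer that the primary standard errors are definitely inflated, that the trial is underpowered, or that the primary test is invalid. The documents support none of these. The first needs a between-site variance that they do not give, the second is contradicted by step 1, and the third mistakes mild conservatism for loss of type I error control.

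**Conclusion.** The point holds in a limited form.

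- **Primary endpoint: minor.** Site is the only named stratum and is absent from the primary model. If sites differ after adjustment, the SE is at most about 2.6% too large at ICC 0.05 and 5.4% at ICC 0.10, a cost of about 1 to 2 points of power; at ICC 0 the cost is nil. Type I error is protected, and the stated 38 per group and 85% power stand. The absence of the term is certain; the size of its effect rests wholly on an assumed ICC.
- **Insulin dose and blood glucose: modest, with the larger potential gain.** Leaving out the outcome's own baseline is inconsistent with how C-peptide and HbA1c are handled. Adding it cuts the SE by about 5 to 29% for an assumed ρ of 0.3 to 0.7; the gain shrinks towards zero if the listed covariates already carry most of the baseline information.

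**What to change.** 1. In 9.1 and 9.4, add study site to the primary ANCOVA as a random intercept, or as a fixed effect with small sites pooled by a rule set before unmasking. Do not use unpooled fixed site effects: with many small sites and a low ICC they can raise the SE. If site is deliberately left out, say why. The sample size need not change.
2. In 9.2, add baseline insulin dose (units/kg) to the insulin-dose model and baseline glucose to the glucose model, keeping the existing covariates.
3. Define both baselines. For insulin dose, state which entry or period of the clinical records in 4.7 supplies the value. For glucose, name the source, for example the screening chemistry panel, and prefer the source that supplies the follow-up values, since the protocol collects glucose in more than one way.

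The cost is a few lines of text and two definitions. No visit or sample is added. A random intercept costs almost nothing if sites turn out not to differ.

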9.2. Secondary Outcome and Analyses

Additional analyses of the primary outcome will include:

- a log rank test of the difference in the hazard function between groups in the first occurrence of a loss of the 2 hour peak C-peptide < 0.2 pmol/ml on a semiannual MMTT (48), and
- longitudinal analyses (45) using mixed effects models with a random intercept and slope of the C-peptide values over the post-treatment period, adjusted for the baseline level of C-peptide. The average intercept and slope will be compared between groups adjusting for age, gender and the baseline $log(Y_{Cp} + 1)$.
- Analyses will also be conducted to adjust for baseline $log(Y_{Cp} + 1)$ and HbA1c levels, and by age, gender and race/ethnicity, as appropriate.
- Analyses will also be conducted to examine the effect of HLA or other genotype and immune phenotypes

Additional secondary objectives are to examine how the GAD-Alum vaccine affects the following:

- Mean C-peptide (as previously described) from the stimulated C-peptide curve over both 2 and 4 hours at 24 months for those age 12 or older
- Mean C-peptide (as previously described) from the stimulated C-peptide curve over 2 hours at 18 months
- HbA1c
- Insulin dose (units/kg)
- Blood glucose
- Number and severity of adverse events
- Hypoglycemia
 - Number of major hypoglycemic events (defined as loss of consciousness, seizure, or requiring assistance from another person because of altered state of consciousness)
 - Reported hypoglycemic events confirmed with capillary blood glucose measurement less than 70 mg/dl.
 - For individuals for whom continuous glucose monitoring data is available
 - Area under the curve and number of events less than 70 mg/dl on the continuous glucose monitoring record
 - Hyperglycemia as measured as the area under the curve and number of events greater than 180 mg/dl on the CGMS record prior to each study visit
 - Glycemia and glycemic variability prior to each MMTT visit
 - The daily mean level of glucose, as well as the levels before and after meals will be computed.
 - Measures of diurnal variability in glucose will be measured by the J-value, standard deviation of glucose values, and the mean amplitude of glycemic excursion (MAGE)

The mean HbA1c, insulin dose (units/kg), and blood glucose over all follow-up values will be compared between groups using a normal errors longitudinal analysis (45). The rates of severe hypoglycemic and adverse events will be computed (total number of events divided by total patient years of follow-up) and the rates compared using a Poisson regression model, allowing for over-dispersion using a quasi-likelihood model as appropriate. Both sets of analyses will be adjusted for age, gender, baseline log(C-peptide+1) and baseline HbA1c.

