4.3. Staggered Enrollment

There will be tiered enrollment by age group. Initially enrollment will be limited to subjects between 16 and 45 years of age. When 20 subjects in this age group randomized to one of the experimental treatment arms have completed three months follow-up, review of the safety data will be done by the FDA and TN DSMB.

If the first formal safety review is acceptable, enrollment will then expand to include subjects age 10 to 45. When 20 subjects between the ages of 10 and 15 randomized to one of the experimental treatment arms have completed three months follow-up, a second review of the safety data will be done by the FDA and TN DSMB.

If this second formal safety review is acceptable, enrollment will then expand to include subjects age 3-45.

In order to maintain similar proportions in this study to other TrialNet studies, enrolment of those age 16 or above may be closed when about 70 such subjects have been enrolled, or 55% of the planned sample size for this trial. Then the remaining subjects would be limited to younger age groups.

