APPENDIX 1 - Schedule of Assessments

NOTE: The schedule for these assessments may vary as appropriate according to the subject's age and body weight. At no time will the blood draw volume exceed 3ml/kg for a single draw and 7ml/kg over a 6 week period for subjects <18 years old.

¹ The target date for the 2^{nd} and 3^{rd} study drug administration will be set in accordance with the previous dose so that the first and second doses will be 4 weeks apart and the third dose will be 8 weeks later. Similarly, the visit target dates after the 2^{nd} and 3^{rd} study drug administration will be scheduled in relation to the actual date the injection was done.

² A 2 hour MMTT will be done for subjects less than age 12.

³ With permission of subject

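### The 24-month 2-hour C-peptide secondary endpoint is limited to age 12 or older, although children under 12 have a 2-hour test at that visit (minor; a free improvement)

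*Protocol*

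**What the plan says.** Protocol section 9.2 names two later time points for mean C-peptide as secondary objectives. The 24-month item is the mean "from the stimulated C-peptide curve over both 2 and 4 hours at 24 months for those age 12 or older". The 18-month item is the mean "from the stimulated C-peptide curve over 2 hours at 18 months", with no age restriction. The primary outcome in section 9.1 is the same 2-hour measure, taken "over the first 2 hours of a mixed meal glucose tolerance test conducted at the one-year visit", also with no age restriction.

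The schedule in Appendix 1 places the 4-hour mixed meal tolerance test (MMTT) at screening and at month 24, and a 2-hour test at the visits in between. Note 2, attached to the 4-hour row, reads: "A 2 hour MMTT will be done for subjects less than age 12".

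Children under 12 can enter. Section 4.3 says that after two acceptable safety reviews "enrollment will then expand to include subjects age 3-45".

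Section 9.2 also plans "mixed effects models with a random intercept and slope of the C-peptide values over the post-treatment period" and a log rank test of time to loss of 2-hour peak C-peptide. Neither has an age limit.

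**The concern.** The age limit makes sense for the 4-hour mean, because children under 12 do not have a 4-hour curve. It does not fit the 2-hour mean, because those children do have a 2-hour curve at month 24. The sentence ties both windows to the one limit, and the protocol gives no separate reason to restrict the 2-hour measure.

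The same 2-hour mean is therefore defined in all ages at 12 and 18 months and only in those 12 or older at 24 months. Two things are at stake. The named endpoint loses some precision although the data are already collected. And anyone who sets its result beside the 12- or 18-month mean is comparing different populations. No other listed endpoint gives a 24-month 2-hour mean for the youngest patients.

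**Working it through.** **Text check.** The passages, set side by side:

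| Analysis | C-peptide measure | Age limit as written | 2-hour data collected under 12? |
|---|---|---|---|
| Primary, 12 months (9.1) | 2-hour mean | none | yes |
| Secondary, 18 months (9.2) | 2-hour mean | none | yes |
| Secondary, 24 months (9.2) | 2-hour mean | 12 or older | yes (Appendix 1, note 2) |
| Secondary, 24 months (9.2) | 4-hour mean | 12 or older | no 4-hour curve |
| Mixed-effects model (9.2) | C-peptide over the post-treatment period | none | yes |
| Log rank test (9.2) | 2-hour peak | none | yes |

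Only the third row has a limit that the schedule does not require.

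**The plan's own figure.** The protocol gives no sample size or power for the 24-month endpoint. Its figure for the primary outcome (section 9.4) is 38 evaluable patients per group for 85% power at one-sided 0.025, with log-scale placebo mean 0.248, SD 0.179 and a 60% increase on the original scale.
- Placebo mean on the original scale: exp(0.248) − 1 = 0.2815.
- Difference on the log scale: ln(1 + 1.6 × 0.2815) − 0.248 = 0.1238.
- n per group = 2 × (0.179/0.1238)² × (1.960 + 1.036)² ≈ 37.5, rounded up to 38. Power at 38 is 85.4%. The stated figure reproduces.

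**How many children could be affected.** The number under 12 is not stated, so it is an assumption shown as a range.
- Enrolment at age 16 or above "may be closed when about 70 such subjects have been enrolled, or 55% of the planned sample size". If the cap is reached, 126 − 70 = 56 places (44%) go to under-16s. That count includes ages 12 to 15, who are not affected.
- Under-10s enter only after 20 patients aged 10 to 15 on the two active arms have three months of follow-up. With equal allocation to three arms, that means about 20 × 3/2 = 30 randomised at ages 10 to 15, leaving about 56 − 30 = 26 places for under-10s.
- The lower end is 0, since the younger tiers might open late or not at all.

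**Effect on precision.** With k children excluded, spread evenly over the arms and with the same residual SD, the standard error is multiplied by √(126/(126 − k)). A common 10% loss cancels from this ratio. The power column uses 0.9 × (126 − k)/3 per group with the primary outcome's planning effect and SD, for illustration only.

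| k excluded | SE factor | Evaluable per group | Illustrative power |
|---|---|---|---|
| 0 | 1.00 | 37.8 | 85% |
| 12 | √(126/114) = 1.05 | 34.2 | 82% |
| 30 | √(126/96) = 1.15 | 28.8 | 75% |
| 56 | √(126/70) = 1.34 | 21.0 | 61% |

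The last row needs the cap to be reached and every under-16 to be under 12. It is a limit, not an expectation.

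**The case against.** The strongest reply is that little is lost. A reader might infer that the youngest children drop out of the 24-month assessment altogether, or that the trial's evidence on durability is confounded by a change of population. The documents do not support that. The mixed-effects model is the protocol's own analysis of change over time; it and the log rank test use month-24 data from all ages. No formal contrast between the 12-month and 24-month means is planned, so the mismatch arises only when the two results are read side by side. This part of the objection stands and confines the point to one endpoint. It does not remove it: the model compares average intercepts and slopes, which is not the mean at 24 months.

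A second reply is that the limit may be deliberate, marking the group with both windows so that 2-hour and 4-hour means come from the same patients, or that it was meant for the 4-hour curve alone. Either is possible, so a deliberate exclusion of children from the 2-hour mean should not be asserted. But the protocol states neither intention, and the first would still leave no all-age 2-hour mean at 24 months.

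A third reply is that the size is unknown. This also stands. The cap is optional, the tiers delay the youngest, and the documents support no minimum loss.

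**Conclusion.** The point holds in a limited form. Read as written, section 9.2 restricts the 24-month 2-hour mean to patients aged 12 or older when the schedule requires that only for the 4-hour mean. The effect is confined to this secondary endpoint, which has no alpha, sample size or decision rule attached. The primary outcome is untouched.

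The size depends on an unstated number of under-12s, from 0 to about 56 of 126 if the cap is reached, and probably well below the top. With 12 or 30 excluded the standard error rises by about 5% or 15%, assuming even spread over arms and equal residual variance. Severity is minor, and the correction is a free improvement.

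A related gap is that the protocol does not say whether age 12 is judged at entry or at the visit. A child who enters at 10 or 11 could have a 2-hour test at screening and, if age is taken at the visit, a 4-hour test at month 24.

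**What to change.** Split the 24-month item in section 9.2 into two:

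- (a) 2-hour mean C-peptide at 24 months in all subjects, analysed with the primary ANCOVA model: log(Y + 1), adjusted for gender, baseline age and baseline log(Y + 1).
- (b) 4-hour mean C-peptide at 24 months in all subjects who had a 4-hour MMTT at that visit, adjusted for the 2-hour baseline log(Y + 1). A 4-hour test at screening should not be a condition: the planned baseline covariate is the 2-hour value, and requiring one would discard usable curves from children who turn 12 during follow-up.

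State in section 9.2 and in Appendix 1, note 2, whether age 12 is judged at entry or at the visit.

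The cost is one reworded item and one clarifying sentence. No visit, sample or test is added.

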5.4. Administration of GAD-Alum or Alum alone

5.4.1. Dosing

All patients will receive 3 subcutaneous injections of 20ug of GAD65-alum or placebo. The first injection is given at baseline (day 0), the second injection is given 4 weeks later, and the third injection is given at 8 weeks after the second. Dosing will not be done in subjects with a febrile illness within the previous 24 hours. These subjects will be rescheduled for another day within a five day window.

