7.1.2. Injection Site Reactions

In previous studies, injection site reactions occurred in a limited number of patient visits. All reactions were mild and most (in particular, "tenderness") occurred primarily on the day of the "prime" injection and "boost" injection four weeks later. No significant differences were seen between the treatment groups.

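### The one adverse-event comparison the protocol specifies pools all follow-up, so it is insensitive to an excess confined to the injection period; add a pre-specified injection-period comparison beside it

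*Protocol*

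**What the plan says.** Section 9.2 of the protocol lists "Number and severity of adverse events" among the secondary objectives. The same section then gives the analysis: "The rates of severe hypoglycemic and adverse events will be computed (total number of events divided by total patient years of follow-up"). The rates are compared by Poisson regression, "allowing for over-dispersion using a quasi-likelihood model as appropriate", with adjustment for age, gender, baseline C-peptide and baseline HbA1c. It states no time window and no period term.

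On timing, section 5.4.1 puts the first injection at day 0 and says "the second injection is given 4 weeks later, and the third injection is given at 8 weeks after the second", which is day 84 in the Appendix 1 schedule. On follow-up, section 9.4 says "The plan is to follow these patients two years from baseline and for up to 2 additional years post-treatment", the extension depending on residual beta-cell function or immunological effects.

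On what was seen before, section 7.1.2 says of injection-site reactions that most "occurred primarily on the day of the" prime and boost injections. It adds that all were mild and that the treatment groups did not differ significantly.

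**The concern.** Study drug is given during the first 12 weeks, but the rate that is compared is spread over two years or more. Events unrelated to the injections accrue in every arm throughout that time. If GAD-alum caused extra events only around the injections, those events would be set against a much larger background count. The ratio would then sit close to 1 with a confidence interval wide enough to include 1.

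What is at stake is how a finding of no difference in adverse events can be read. The trial plans to enrol children from age 3 after two safety reviews. A statement that adverse-event rates did not differ carries less weight if the only specified comparison had little chance of showing a moderate, short-lived excess. The denominator is written into section 9.2, so this is a choice the protocol has made and not merely a detail it leaves open.

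**Working it through.** The protocol gives no power or precision figure for adverse events, so there is none to reproduce. Its only sample-size calculation concerns C-peptide.

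**Inputs from the protocol**
- 42 participants per arm (section 4.5).
- Injections at days 0, 28 and 84 (section 5.4.1, Appendix 1).
- Planned follow-up of 2 years, 730 days (section 9.4).

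**Assumptions, not in the protocol**
- Injection period: day 0 to 30 days after the third injection, 84 + 30 = 114 days.
- Background: 2 reported events per patient-year (range 1 to 3).
- Dispersion φ: 1 to 2.
- Excess confined to the window, with in-window rate ratio R.
- One active arm against placebo, two-sided 5%, no dropout, no covariate adjustment.

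**Size of the dilution**
- Window fraction f = 114/730 = 0.156.
- Overall ratio = 1 + f(R − 1).
- R = 2 gives 1.16; R = 3 gives 1.31; R = 5 gives 1.62.
- For participants followed for four years, f = 114/1460 = 0.078, and R = 2 gives 1.08.
- The relative excess shrinks by 730/114 = 6.4. That factor depends on the assumed window: 12 weeks in 104 would give 104/12 = 8.7.

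**Power for a doubling at 2 events per patient-year**

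SE(log ratio) = √[φ(1/e₀ + 1/e₁)] and power = Φ(log ratio/SE − 1.96), where e₀ and e₁ are the expected placebo and active counts.

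*Pooled:* e₀ = 42 × 2 × 2 = 168. The excess is 42 × (114/365) × 2 = 26.2, so e₁ = 194.2 and log ratio = ln(1.156) = 0.145.
- φ = 1: SE = 0.105, z = 1.38, power 28%.
- φ = 2: SE = 0.149, z = 0.97, power 16%.

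*Injection period:* e₀ = 26.2, e₁ = 52.5, log ratio = ln 2 = 0.693.
- φ = 1: SE = 0.239, z = 2.90, power 83%.
- φ = 2: SE = 0.338, z = 2.05, power 54%.

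The number of excess events is the same in both analyses (about 26). What differs is the placebo-arm background they are set against: 168 events or 26.

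**Sensitivity to the assumptions** (φ from 2 to 1)

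| In-window ratio | Background per patient-year | Pooled power | Injection-period power |
|---|---|---|---|
| 2 | 1 to 3 | 10-39% | 30-94% |
| 3 | 2 | 47-76% | 93% or more |
| 5 | 2 | 94% or more | over 99% |

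The loss is therefore serious for a doubling, moderate for a tripling and small for a fivefold excess.

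**The case against.** There is a good case for leaving section 9.2 alone, and much of it stands.

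- **The protocol's safety history does not predict an arm difference.** Section 7.1.2 reports mild reactions with no significant group difference, and section 7.1.1 says the same of influenza-like symptoms. All three arms receive three alum injections (section 4.5), so reactions to alum or the needle occur in every arm. Only events of Grade 2 or above go on the adverse-event form (sections 8.1.1 and 8.2), so mild reactions would largely not be counted. The history supports the timing of reactions, not an expected excess.
- **Long follow-up is appropriate for this product.** The intended effect is lasting immune tolerance. Section 3.2.2 reports benefit to 30 months, and the neurological concern in section 3.2.3 has no short time limit. Putting an injection-period comparison ahead of the full rate would push delayed events into the background.
- **The early period is reviewed.** Under section 4.3 the FDA and DSMB review safety when 20 actively treated participants aged 16-45, and later 20 aged 10-15, have three months of follow-up. Section 8.2 has the DSMB review adverse events by arm about every three to six months. No between-arm test is stated for these reviews, so they do not replace the comparison in section 9.2, but the early months are not unexamined.
- **A statistical analysis plan may add windows.** That is common, and section 9.2 does not forbid it. The answer is narrow: the protocol does specify one comparison, and that one has the low sensitivity shown.

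A reader might infer that the pooled ratio is biased, or that an injection-related excess would probably be missed. Neither is supported. The pooled ratio correctly estimates what it defines, and whether an excess is missed depends on a background rate, dispersion and effect size that the protocol does not give.

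**Conclusion.** The point holds as a limit on sensitivity. The only between-arm adverse-event comparison the protocol specifies is a valid measure over all follow-up but a weak one for a moderate excess around the injections. On the stated assumptions, a doubling within 114 days becomes an overall ratio of 1.16, and power is about 16-28% pooled against 54-83% in the window. The window length, background rate, dispersion and size of excess are all assumed.

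The documents do not show that an excess is expected, and they do not support making the injection period the lead safety comparison. What remains is a cheap gain. The side effects the protocol expects are mainly acute, and Appendix 1 already schedules adverse-event assessment at days 14, 28, 35, 84 and 91.

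**What to change.** In section 9.2, keep the rate over all follow-up. Alongside it, and not as the lead comparison, add a pre-specified comparison of adverse-event rates from first injection to a fixed interval after the actual third injection, with events and patient-time both restricted to that period and the same quasi-Poisson model. The 30 days used above is only an illustration; the sponsor should choose the interval before unmasking. Anchoring on the actual date matters because section 6.6 allows each later injection up to 7 days late, counted from the previous one, so the third can fall at day 84 + 14 = 98. State which date closes the window when the third injection is not given. Report the remaining follow-up as a second period so that delayed events stay visible.

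The cost is a few lines of text, one more model and one more table. The short window will hold fewer events, so its estimate will be less precise on the log scale: at 2 events per patient-year, φ = 1 and R = 2, the standard error is 0.239 against 0.105 for the pooled rate. No extra visits are needed.
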